### **3.1.3 Follow Up Phase**

This phase begins when the decision to discontinue study drug is made. Two follow up visits are required, occurring 35 days  $\pm$  7 days from the last dose (X01) and 80 days  $\pm$  7 days from X01 (X02). Follow up visits include targeted physical examination, laboratory tests, tumor assessments, adverse event and concomitant medication assessments, and PRO instrument collection. Additional details and requirements are outlined in [Table 5.1-4](#). After completion of the first two follow-up visits, subjects will be followed every 3 months for survival, as outlined in [Table 5.1-4](#).

Subjects who discontinue study drug for reasons other than radiographic disease progression will continue to have tumor assessments (if clinically feasible) according to the schedule in [Table 5.1-2](#) and [Table 5.1-3](#) until progression.

Subjects will be followed for drug-related toxicities until these toxicities resolve, return to baseline or are deemed irreversible. All adverse events will be documented for a minimum of 100 days after the last dose of study drug.

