### 3. Age and Reproductive Status

- a) Males and Females, ages  $\geq 18$  years of age
- b) Women of childbearing potential (WOCBP) must have a negative serum or urine pregnancy test (minimum sensitivity 25 IU/L or equivalent units of HCG) within 24 hours prior to the start of study drug.
- c) Women must not be breastfeeding
- d) Women of childbearing potential (WOCBP) must agree to follow instructions for method(s) of contraception as indicated in the informed consent form, for the duration of treatment with study drug(s) [nivolumab or sorafenib] plus approximately 5 half-lives of the study drug(s) [nivolumab or sorafenib] plus 30 days (duration of ovulatory cycle):
  - i) Subjects randomized to nivolumab: total of 5 months post-treatment completion
  - ii) Subjects randomized to sorafenib: total of 40 days post-treatment completion
- e) Males who are sexually active with WOCBP must agree to follow instructions for method(s) of contraception as indicated in the informed consent form, for the duration of treatment with study drug (s) [nivolumab or sorafenib] plus approximately 5 half-lives of the study drug(s) [nivolumab or sorafenib] plus 90 days (duration of sperm turnover):
  - i) Subjects randomized to nivolumab: total of 7 months post-treatment completion
  - ii) Subjects randomized to sorafenib: total of 100 days post-treatment completion
- f) Azoospermic males and WOCBP who are continuously not heterosexually active are exempt from contraceptive requirements. However they must still undergo pregnancy testing as described in this section.

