FACT-Hep	See Note	To be completed on Cycle 1, Day 1, then every other cycle thereafter

Table 5.1-3: On treatment Period Procedural Outline - Sorafenib (CA209459)		
Procedure	During Treatment: (Cycle = 2 weeks)  Cycle 1 - Day 1 (C1, D1), Cycle 2 - Day 1 (C2 D1), (and every cycle thereafter)	Notes
		Cycle 3, Day 1; Cycle 5, Day 1, etc.)
Health care resource use (HCRU)	X	
Clinical Drug Supplies		
Contact central randomization IVRS / Dispense Study Drug	X	Within 3 days from randomization, the subject must receive the first dose of study medication.  IVRS should be contacted at each visit for provision of 2 week supply of sorafenib.

Table 5.1-4: Follow-Up Procedural Outline - all subjects (CA209459)			
Procedure	Follow Up, Visits 1 and 2 (X visits)a	Survival Follow Up Visits (Y visits)b	Notes
Safety Assessments			
Targeted Physical examination	X		Targeted examination must include at a minimum the following body systems: Cardiovascular Gastrointestinal Pulmonary Skin
Adverse Events Assessment	X	X	
Review of Concomitant Medications	X		
Review of Subsequent Cancer Therapy	X	X	
Laboratory Tests	X		Performed locally: CBC w/differential and platelet count, LFTs (ALT, AST, total bilirubin, alkaline phosphatase), alpha fetoprotein (AFP), BUN or serum urea level, albumin, creatinine, Ca+, Mg++, Na+, K+, Cl-, LDH, amylase, lipase, glucose, TSH (Reflex to free T3 and free T4 if TSH abnormal. Total T3/T4 are acceptable if free T3/T4 are not available.) To be done at FU1. To be repeated at FU2 if study related toxicity persists.
Pregnancy Test (WOCBP only)	X		Serum or urine pregnancy test (minimum sensitivity 25 IU/L or equivalent units of HCG).

Table 5.1-4: Follow-Up Procedural Outline - all subjects (CA209459)			
Procedure	Follow Up, Visits 1 and 2 (X visits)a	Survival Follow Up Visits (Y visits)b	Notes
Coagulation profile	X		Include International Normalized Ratio (INR). If INR cannot be done by the local laboratory, then Prothrombin Time (PT) may be provided instead
Efficacy Assessments			

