Tumor imaging assessment	See Note	See Note	
Tumor imaging assessments during Follow Up and Survival Follow up is required for subjects that have discontinued treatment prior due to reason other than radiologic disease progression.
 
Tumor imaging assessments will occur 8 weeks from the date of randomization (+/- 1 wk), then every 8 weeks (+/- 1 wk) thereafter up to 48 weeks, then it will be every 12 weeks (+/- 1 week) until disease progression.
 
CT of the chest, CT or MRI of abdomen, and pelvis with IV contrast, including required tri-phasic CT of the liver should be performed. CT chest without contrast or MRI abdomen/pelvis is acceptable if CT is contraindicated. Modality (CT or MRI) used at baseline should be used across all imaging timepoints. Bone scan is required if clinically indicated.
 
Subjects with a history of brain metastasis may have surveillance MRI approximately every 12 weeks from the date of first dose, or sooner if clinically indicated

Other Assessments			
PK/IMG sampling	X		To be collected for nivolumab subjects only. See Section 5.5.1

Table 5.1-4: Follow-Up Procedural Outline - all subjects (CA209459)			
Procedure	Follow Up, Visits 1 and 2 (X visits)a	Survival Follow Up Visits (Y visits)b	Notes
Outcomes Research Assessment			The EQ-5D and FACT-Hep should be administered at the start of the visit, before the subject sees the physician and before any study related procedures are done
EQ-5D-3L	X	X	EQ-5D to be assessed during clinical visit or via a phone for survival follow-up visits
FACT-Hep	X	X	FACT-Hep to be assessed during clinical visit or via a phone for survival follow-up visits
Health care resource use (HCRU)	X		Health Care Resource Use (HCRU) to be assessed during clinical visit
Subject Status			
Survival Status		X	Every 3 months after FU 2; may be accomplished by visit or phone contact

a X visits occur as follows: X01 = 35 days ± 7 days from last dose, X02 = 80 days ± 7 days from X01

b S, Survival visits continue every 3 months after X visits

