### **6.2.1 Nonserious Adverse Event Collection and Reporting**

The collection of nonserious AE information should begin at initiation of study drug. Nonserious AE information should also be collected from the start of a placebo lead-in period or other observational period intended to establish a baseline status for the subjects.

Nonserious AEs should be followed to resolution or stabilization, or reported as SAEs if they become serious (see [Section 6.1.1](#)). Follow-up is also required for nonserious AEs that cause interruption or discontinuation of study drug and for those present at the end of study treatment as appropriate. All identified nonserious AEs must be recorded and described on the nonserious AE page of the CRF (paper or electronic).

All nonserious adverse events (not only those deemed to be treatment-related) should be collected continuously during the treatment period and for a minimum of 100 days following the last dose of study treatment.

Completion of supplemental CRFs may be requested for AEs and/or laboratory abnormalities that are reported/identified during the course of the study.

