#### **8.4.3 Safety Analyses**

The safety analysis will be performed in all treated subjects. Descriptive statistics of safety will be presented using National Cancer Institute (NCI) Common Terminology Criteria for Adverse Events (CTCAE) version 4.0 by treatment arm. All on-treatment AEs, drug-related AEs, SAEs and drug-related SAEs will be tabulated using worst grade per NCI CTCAE v 4.0 criteria by system organ class and preferred term. On-study lab parameters including hematology, coagulation, chemistry, liver function and renal function will be summarized using worst grade per NCI CTCAE v 4.0 criteria.

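### The main laboratory panel is repeated at the second follow-up visit only for persisting study-related toxicity, so FU2 laboratory data come from a group selected by a relatedness judgement

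*Protocol*

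**What the plan says.** **Laboratory rule.** The Laboratory Tests row of Protocol Table 5.1-4 covers blood counts, liver tests, electrolytes, pancreatic enzymes, glucose and TSH. Its note reads "To be done at FU1. To be repeated at FU2 if study related toxicity persists". The table applies to all subjects, with no separate rule by arm. The coagulation profile, targeted physical examination and adverse event assessment are marked for both X visits without this condition.

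**Section 3.1.3.** "Follow up visits include targeted physical examination, laboratory tests, tumor assessments" is stated there for the follow-up visits with no condition attached. The same section then sends the reader to Table 5.1-4 for further details and requirements.

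**Timing.** The footnote to Table 5.1-4 gives "X01 = 35 days ± 7 days from last dose" and "X02 = 80 days ± 7 days from X01". The synopsis, and SAP Sections 2.1 and 4.2, place follow-up visit 2 at about 100 days from the last dose.

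**Adverse events.** Under Protocol 6.2.1, nonserious events "should be collected continuously during the treatment period and for a minimum of 100 days following the last dose of study treatment". Section 6 has a physician determine causal relationship. Section 6.3 requires clinically significant laboratory results to be recorded as adverse events.

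**Other laboratory provisions.** Section 5.3 has laboratory toxicities followed locally until they resolve, return to baseline or are judged irreversible, and allows extra tests when clinically indicated.

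**Analysis.** Protocol 8.4.3: "On-study lab parameters including hematology, coagulation, chemistry, liver function and renal function will be summarized using worst grade per NCI CTCAE v 4.0 criteria". SAP Sections 6.1 and 7.6.11 leave the laboratory evaluation period and tables to the Core Safety SAP, which is not among the documents.

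**The concern.** The condition in Table 5.1-4 has two parts, and each selects. The toxicity must persist, so the repeat panel goes to subjects who already had a problem; a subject who was clear at FU1 and later develops a silent liver, thyroid, pancreatic or hematologic abnormality does not qualify. The toxicity must also be study related, which is a judgement made with the treatment known.

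Laboratory findings differ from symptoms in that they exist in the data only if someone draws blood. An abnormality that is never tested for enters neither the worst-grade table nor the adverse event listing. FU2 panel results also cannot be read as a sample of all subjects at that visit. If the share of subjects judged to have persisting related toxicity differed between arms, detection of late abnormalities would differ too, whatever the true rates.

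**Working it through.** **1. The plan's own figure for FU2.** The stated value is about 100 days after the last dose. From the Table 5.1-4 windows:

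- X01 = 35 ± 7, so day 28 to 42.
- X02 = X01 + (80 ± 7), so 73 to 87 days after X01.
- Earliest: 28 + 73 = 101. Nominal: 35 + 80 = 115. Latest: 42 + 87 = 129.

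The stated figure is not reproduced. Of the 15 × 15 = 225 whole-day combinations of the two windows, none puts X02 on or before day 100.

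**2. Days of the 100-day window left after FU1.** The formula is 100 − X01.

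| X01 | Days left |
|---|---|
| Day 28 | 72 |
| Day 35 (nominal) | 65 |
| Day 42 | 58 |

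**3. What the condition causes, and what it does not.** X02 lies beyond day 100 for every permitted combination. The 58 to 72 days without a scheduled panel inside the window are therefore due to visit spacing, and removing the condition would leave them unchanged. What the condition does remove is the panel at day 101 to 129 in everyone without a persisting related toxicity. That panel could find abnormalities that arose after FU1 and are still present at X02.

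**4. What the other provisions cover.**

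| Abnormality first arising after FU1 | Provision that would find it |
|---|---|
| Coagulation | Unconditional at both X visits |
| Symptomatic or clinically suspected | Extra tests when indicated (Section 5.3), examination and AE assessment at X02 |
| Continuation of a known toxicity | Local follow-up (Section 5.3) and the FU2 condition itself |
| Silent and new, on the main panel | No scheduled test |

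Only the last row is left open.

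**5. Could it create a between-arm difference?** The documents give no rate of late abnormality and no share of subjects tested at FU2, so this is an illustration on assumed values. Let p be the true proportion with a late abnormality, equal in both arms, and f the share tested, taken as independent of the abnormality. The detected proportion is p × f, and the spurious difference is p × (f₁ − f₂).

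| p | f equal in both arms | f = 10% v 30% |
|---|---|---|
| 5% | 0 | 1 point (0.5% v 1.5%) |
| 10% | 0 | 2 points (1% v 3%) |
| 20% | 0 | 4 points (2% v 6%) |

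The arm with more testing shows more abnormality. With equal testing there is no difference.

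**The case against.** The strongest case against the point is that the rule is identical in both arms, known toxicities are followed anyway, clinically indicated tests are allowed, and Section 3.1.3 defers to Table 5.1-4, so the note is a detail and not a contradiction. Most of this stands. The deferral makes the conflict between the two sections a mild one. Table 5.1-4 does not name who decides on the FU2 panel; that it rests on a treating physician who knows the arm is an inference from Section 6 and the open-label design. None of it reaches the silent new abnormality.

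Three stronger readings are tempting and should not be drawn.

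- **That late nivolumab toxicity is understated.** The contraception rules allow about five half-lives plus 30 days for women. For sorafenib the rule is "Subjects randomized to sorafenib: total of 40 days post-treatment completion", which implies 40 − 30 = 10 days of drug; for nivolumab 5 months less 30 days is about 122 days. FU1 at day 28 to 42 is then after sorafenib's period but only 23% to 34% of the way through nivolumab's (28/122 and 42/122). This makes differential detection plausible, but it assumes that laboratory toxicity follows five half-lives. It also ignores the opposite mechanism: if more nivolumab toxicity persisted, more nivolumab subjects would be tested at FU2, which would raise that arm's worst grades.
- **That a stated fraction of laboratory events is lost because of this rule.** The gap inside the window comes from spacing, as step 3 shows. A share of time at risk is also not a share of missed events, because prompted tests still detect some.
- **That the by-arm safety tables are biased as they stand.** Whether samples after FU1 or after day 100 enter those tables depends on the Core Safety SAP.

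**Conclusion.** The point holds in a limited form. FU2 results on the main panel are collected selectively, on a criterion that includes relatedness in an open-label trial, and silent abnormalities first arising after FU1 have no scheduled panel. Section 3.1.3 and Table 5.1-4 do not say the same thing, and the FU2 visit computes to day 115 (101 to 129) where other sections say about 100.

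The size of any effect on the safety comparison cannot be fixed from the documents. Under the assumed values above it runs from 0 to 4 percentage points, and a non-zero value needs the share tested to differ by arm, which is not documented. The primary analysis of overall survival is untouched. This is an inexpensive improvement to safety ascertainment, not a threat to the trial's main conclusion.

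**What to change.** **Protocol.** Reconcile Table 5.1-4 with Section 3.1.3 so that whether the panel is collected at X02 does not depend on attribution and is the same for all subjects in both arms. In the same edit, reconcile the FU2 timing between the synopsis and the Table 5.1-4 footnote; until that is settled, a panel at X02 falls after day 100 and does not fill the gap inside the window. The cost is one more local panel. X02 is already required, and coagulation blood (and nivolumab pharmacokinetic blood) is already drawn there, so no new visit or venipuncture is needed.

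**SAP, for data collected under the conditional rule.** SAP Section 7.10 records the database lock for the final survival analysis as June 2019, so for those data only the analysis can change.

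- Keep the planned worst-grade table. Replacing it with data through FU1 would discard toxicity actually observed later.
- Add a supplementary by-arm worst-grade table limited to samples through FU1, the last visit at which the panel is scheduled for everyone.
- Flag FU2 panel results as selectively collected, and report by arm how many subjects had them.
- State how this fits the laboratory evaluation period in the Core Safety SAP.

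The cost is a sentence or two of SAP text and the programming of one table.

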### **5.1.1 Retesting During Screening Period**

Retesting of laboratory parameters and/or other assessments within any single Screening period will be permitted (in addition to any parameters that require a confirmatory value).

Any new result will override the previous result (ie, the most current result prior to Randomization) and is the value by which study inclusion will be assessed, as it represents the subject's most current, clinical state.

Laboratory parameters and/or assessments that are included in [Table 5.1-1](#), Screening Procedural Outline may be repeated in an effort to find all possible well-qualified subjects. Consultation with the Medical Monitor may be needed to identify whether repeat testing of any particular parameter is clinically relevant.

## **5.2 Study Materials**

- NCI CTCAE version 4.0
- BMS-936558 (nivolumab) Investigator Brochure
- Sorafenib SmPC
- Pharmacy Binder
- Laboratory manuals for collection and handling of blood (including biomarker and immunogenicity) and tissue specimens
- Site manual for operation of interactive voice response system, including enrollment worksheets
- Manual for entry of local laboratory data
- Pregnancy Surveillance Forms
- Serious Adverse Events (or eSAE) case report forms
- EQ-5D-3L and FACT-Hep questionnaires
- CA209459 Imaging Manual

## **5.3 Safety Assessments**

At baseline, a medical history will be obtained to capture relevant underlying conditions. The baseline examinations should include signs and symptoms, weight, height, ECOG Performance Status, BP, HR, temperature, respiratory rate, and should be performed within 14 days prior to first dose except where noted in [Table 5.1-1](#). Concomitant medications will also be collected from within 14 days prior to first dose and through the follow up period (See [Table 5.1-1](#), [Table 5.1-2](#), [Table 5.1-3](#) and [Table 5.1-4](#)). Baseline laboratory assessments should be done within 14 days prior to randomization and include (see [Table 5.1-1](#)):

- CBC w/differential and platelet count,
- LFTs (ALT, AST, total bilirubin, alkaline phosphatase),
- alpha fetoprotein (AFP),
- BUN or serum urea level,

- albumin,
- creatinine,
- Ca+,
- Mg++,
- Na+,
- K+,
- Cl,
- LDH,
- glucose,
- amylase,
- lipase,
- TSH, (Reflex to free T3 and free T4 if TSH abnormal. Total T3/T4 are acceptable if free T3/T4 are not available),
- coagulation profile (INR or PT), and
- urinalysis

Baseline serology should be obtained within 28 days prior to randomization and should include: Hep B surface antigen, Hep B surface antibody, Hep B core antibody, Hep B DNA viral load, Hep C viral load, Hep C antibody, and Hep D antibody.

Baseline 12-lead ECG and 2-D Echocardiogram are required, and should be performed locally within 14 days prior to first dose. Pregnancy testing for WOCBP (done locally) to be done at screening, within 24 hours prior to first dose, and then monthly regardless of dosing schedule, and at each safety follow up visit.

Subjects will be evaluated for safety if they have received any study drug. Toxicity assessments will be performed continuously during the treatment phase. During the safety follow-up phase (Table 5.1-4) toxicity assessments should be done in person. Once subjects reach the survival follow-up phase, either in-person visits or documented telephone calls to assess the subject's status are acceptable.

Adverse events and laboratory values will be graded according to the NCI-CTCAE version 4.0.

On treatment weight, ECOG performance status, vital signs, laboratory tests and targeted physical examinations may be performed within 72 hours prior to nivolumab dosing, or during the Day 1 visit (ie, day of clinic visit) or subjects randomized to sorafenib. In addition, vital signs can also be taken as per institutional standard of care prior to; during and after the nivolumab infusion. The start and stop time of the nivolumab infusion should be documented. If there are any new or worsening clinically significant changes since the last exam, report changes on the appropriate non-serious or serious adverse event page.

Blood pressure monitoring frequency for subjects randomized to sorafenib should follow local standards of care as guided by the locally approved sorafenib product label or applicable SmPC.

Additional measures, including non-study required laboratory tests, should be performed as clinically indicated or to comply with local regulations. Laboratory toxicities (eg, suspected drug induced liver enzyme elevations) will be monitored during the follow-up phase via on site/local labs until all study drug related toxicities resolve, return to baseline or are deemed irreversible.

If a subject shows pulmonary-related signs (eg, hypoxia, fever) or symptoms (eg, dyspnea, cough) consistent with possible pulmonary adverse events, the subject should be immediately evaluated to rule out pulmonary toxicity. An algorithm for the management of suspected pulmonary toxicity for subjects randomized to nivolumab can be found in [Appendix 5](#).

Some of the previously referred to assessments may not be captured as data in the eCRF. They are intended to be used as safety monitoring by the treating physician. Additional testing or assessments may be performed as clinically necessary or where required by institutional or local regulations.

### **5.3.1 Imaging Assessment for the Study**

Images will be submitted to an imaging core lab for central review. Sites will be trained prior to scanning the first study subject. Image acquisition guidelines and submission process will be outlined in the CA209459 Imaging Manual to be provided by the core lab.

Any incidental findings of potential clinical relevance that are not directly associated with the objectives of the protocol should be evaluated and handled by the Study Investigator as per standard medical/clinical judgment.

- **CT/MRI**

Contrast-enhanced Computed Tomography (CT) scans acquired on dedicated CT equipment is preferred for this study. The CT with contrast of the chest, abdomen and pelvis including contrast-enhanced triphasic CT of the abdomen is to be performed for tumor assessments until disease progression is documented or treatment is discontinued (whichever occurs later). CT scans should be acquired with 5 mm slices with no intervening gap (contiguous).

Should a subject have a contraindication for IV contrast, a non-contrast CT of the chest and a contrast-enhanced MRI of the abdomen and pelvis may be obtained. MRIs should be acquired with slice thickness of < 5 mm with no gap (contiguous).

Every attempt should be made to image each subject using an identical acquisition protocol on the same scanner for all imaging time points.

- **Note: Use of CT component of a PET/CT scanner:**

Combined modality scanning such as with FDG-PET/CT is increasingly used in clinical care, and is a modality/technology that is in rapid evolution; therefore, the recommendations outlined here may change rather quickly with time. At present, low dose or attenuation correction CT portions of a combined FDG-PET/CT are of limited use in anatomically based efficacy assessments and it is therefore suggested that they should not be substituted for dedicated diagnostic contrast enhanced CT scans for anatomically based RECIST measurements. However, if a site can document that the CT performed as part of a FDG-PET/CT is of identical diagnostic quality to a diagnostic CT (with IV and oral contrast)

then the CT portion of the FDG-PET/CT can be used for RECIST 1.1 measurements. Note, however, that the FDG-PET portion of the CT introduces additional data which may bias an investigator if it is not routinely or serially performed.

- **MRI Brain**

MRI of brain is required at screening in order to rule out active metastatic disease in subjects with a history of brain metastasis. Subjects with a history of brain metastasis may have surveillance MRI approximately every 12 weeks, or sooner if clinically indicated. MRI brain scans during on-study treatment and follow up periods are required only if there is a prior history of lesions present at Screening, or as clinically indicated for new signs and symptoms that suggest central nervous system (CNS) involvement.

